10. EFFICACY ANALYSES

10.1 Primary Efficacy Variable(s) and Analysis

The primary efficacy analysis will be conducted over the subjects in the Full Analysis Set that are randomized to Treatment Sequence 1 (A/B) or 2 (B/A) to evaluate of the efficacy of SC administration of C1 esterase inhibitor [human] liquid for injection compared to placebo.

The primary efficacy endpoint is defined as the normalized number of angioedema attacks during a treatment period. The NNA is expressed as the number of attacks per month (ie, 30.4 days) of exposure:

NNA = 30.4 x (number of attacks during treatment period)/(days of treatment period)

If a subject discontinues during the treatment period, the denominator of the NNA will be the days on treatment for that subject; this is equivalent to the last observation carried forward imputation method to impute the missing information following the subject's discontinuation.

To test the hypothesis that the NNA of C1 esterase inhibitor [human] liquid for injection is greater than or equal to the NNA of placebo, and the alternative hypothesis that the NNA of C1 esterase inhibitor [human] liquid for injection is less than the NNA of placebo as below:

H_{0:} μ _{C1 INH} - μ placebo ≥ 0 VS H_{1:} μ _{C1 INH} - μ placebo < 0

A linear mixed effect model will be performed to analyze the primary efficacy endpoint with period, sequence, use of prophylactic therapy with C1 INH, which is derived by long-term prevention with C1 INH at randomization, and treatment as fixed effects, and subject nested within sequence as a random effect. If the variance-covariance matrix of random effects is not positive definite, a mixed effect model with the same fixed effects and subject nested within sequence as repeated measurements will be performed instead; the repeated measurement is equivalent to the random effect in terms of statistical testing and point estimates of coefficients of fixed effects, however, the variance covariance matrix of random effects will not be estimated. The mean treatment difference ($\mu_{C1 \text{ INH}} - \mu_{placebo}$) will be estimated with a 95% CI provided. The upper confidence bound of 95% CI must be less than 0 in order for C1 INH to be considered superior to the placebo.

A summary of NNA during each treatment period by treatment sequences will be provided for the Full Analysis Set.

In addition, the NNA will be presented graphically for subjects randomized to the first 2 treatment sequences (A/B or B/A) in the Full Analysis Set, with the observed NNA on the vertical axis and the treatment periods (with assigned treatments) on the horizontal axis.

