9.8 Efficacy Analyses

9.8.1 Primary Efficacy Endpoint

The primary efficacy endpoint is defined as the NNA during a treatment period. The NNA is expressed as the number of attacks per month (ie, 30.4 days) of exposure:

$$\text{NNA} = 30.4 \times (\text{number of attacks during treatment period}) / (\text{days of treatment period})$$

If a subject discontinues during the treatment period, the denominator of the NNA will be the days on treatment for that subject; this is equivalent to the last observation carried forward imputation method to impute the missing information following the subject's discontinuation.

The primary efficacy analysis will be conducted for the subjects in the Full Analysis Set (Section 9.7) that are randomized to Treatment Sequence 1 (A/B) or 2 (B/A) to evaluate of the efficacy of SC administration of C1 esterase inhibitor [human] liquid for injection compared to placebo. The null hypothesis to be tested is that the NNA of C1 esterase inhibitor [human] liquid for injection is greater than or equal to the NNA of placebo, and the alternative hypothesis is that the NNA of C1 esterase inhibitor [human] liquid for injection is less than the NNA of placebo as below:

$$H_0: \mu_{\text{C1 INH}} - \mu_{\text{placebo}} \geq 0 \text{ vs}$$

$$H_1: \mu_{\text{C1 INH}} - \mu_{\text{placebo}} < 0$$

The primary efficacy endpoint will be analyzed by using a linear mixed effect model with period, sequence, stratification factor (use of prophylactic therapy with C1 INH), and treatment as fixed effects, and subject nested within sequence as a random effect. The mean treatment difference ($\mu_{\text{C1 INH}} - \mu_{\text{placebo}}$) will be estimated with a 95% CI.

To assess any carryover effect, a sensitivity analysis will exclude from the evaluation of the NNA any attacks occurring within the first 2 weeks of Treatment Period 2 for both sequences when carryover is suspected to be maximal. Since carryover should occur only with the A/B treatment sequence, its effect (if present) will be to spread C1 esterase inhibitor [human]

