9.8.2 Secondary Efficacy Endpoints

9.8.2.1 Key Secondary Efficacy Endpoints

1. The proportion of subjects meeting the criterion of at least a 50% reduction in the NNA during the 2000 IU C1 esterase inhibitor [human] liquid for injection treatment period relative to the placebo period.
2. The NNA excluding the first 2 weeks of each treatment period.
3. The proportion of subjects meeting the criterion of at least a 50% reduction in the NNA for the 2000 IU C1 esterase inhibitor [human] liquid for injection treatment period relative to the placebo period excluding the first 2 weeks of each treatment period.

Key secondary efficacy endpoints 1 and 3 are defined as achieving a $\geq 50\%$ reduction in the NNA (P_R) during the 2000 IU C1 esterase inhibitor [human] liquid for injection treatment period relative to the placebo period. Key secondary endpoints 1 and 3 will be analyzed as the proportion of subjects meeting criterion P_R . The null hypothesis is that P_R is less than or equal to 0.2, and the alternative hypothesis is that P_R is greater than 0.2. The proportion meeting criterion P_R will be estimated with an exact 95% CI. The lower limit of the 95% CI for the proportion will be compared with 0.2. This is equivalent to testing the null hypothesis against the alternative hypothesis at a 1-sided alpha level of 0.025 using the normal approximation to the binomial distribution.

Analysis of key secondary endpoint 2 will follow the same methods (ie, the linear mixed effect model) used for the primary efficacy endpoint.

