4.5 Full Analysis Set

All subjects in the Safety Set who have at least 1 post-baseline (i.e., randomization) primary efficacy assessment will be included in the full analysis set.

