4.6 Per-protocol Set

All subjects in the Full Analysis Set who complete scheduled primary assessments for 6 study weeks and who do not have pre-defined protocol deviations that may affect the primary efficacy endpoint will be included in the Per-protocol Set. Refer to Appendix 19.4 for the protocol deviations that exclude subjects from the Per-protocol Set.

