10.2 Key Secondary Efficacy Variable(s) and Analysis

The key secondary efficacy variables are listed as following:

- 1. The proportion of subjects meeting the criterion of at least a 50%, 70%, 90% and 100% reduction in the NNA during the 2000 IU C1 esterase inhibitor [human] liquid for injection treatment period relative to the placebo period.
- 2. The NNA excluding the first 2 weeks of each treatment period.
- 3. The proportion of subjects meeting the criterion of at least a 50%, 70%, 90% and 100% reduction in the NNA for the 2000 IU C1 esterase inhibitor [human] liquid for injection treatment period relative to the placebo period excluding the first 2 weeks of each treatment period.

Key secondary efficacy endpoints 1 and 3 are defined as achieving a \geq 50% reduction in the NNA (P_R) during the 2000 IU C1 esterase inhibitor [human] liquid for injection treatment period relative to the placebo period.

The Key secondary endpoints 1 and 3 will be analyzed as the proportion of subjects meeting the above clinical response criterion (P_R). The analysis will be conducted over the Full Analysis Set from the first two treatment sequences. The null hypothesis is that P_R is less than or equal to 0.2, and the alternative hypothesis is that P_R is greater than 0.2 as below:

$$H_{0:} P_{R} \leq 0.2$$
vs
$$H_{1:} P_{R} > 0.2$$

The proportion P_R will be estimated with an exact 95% CI. The lower limit of the 95% CI for the proportion will be compared with 0.2. This is equivalent to testing the null hypothesis against the alternative hypothesis at a 1-sided alpha level of 0.05 using the binomial distribution.

Analysis of key secondary endpoint 2 will follow the same methods (ie, the linear mixed effect model) used for the primary efficacy endpoint.

The key secondary analyses will be performed using the Full Analysis Set and the Per-protocol Set.

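### Key secondary 1 sets no minimum exposure, so a B/A subject who stops active treatment after a few attack-free days counts as a responder; the effect on the test is modest

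*SAP*

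**What the plan says.** **Rate for early stoppers.** NNA is 30.4 times the number of attacks divided by the days of the treatment period. For early stoppers SAP 10.1 states: "If a subject discontinues during the treatment period, the denominator of the NNA will be the days on treatment for that subject". Protocol 9.8.1 has the same rule and adds that "this is equivalent to the last observation carried forward imputation method to impute the missing information following the subject's discontinuation". Neither document sets a minimum number of days.

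**Endpoint.** Protocol 9.8.2.1 defines key secondary 1 as "The proportion of subjects meeting the criterion of at least a 50% reduction in the NNA during the 2000 IU C1 esterase inhibitor" treatment period, relative to the placebo period. SAP 10.2 also lists 70%, 90% and 100% reductions, but P_R is the 50% criterion. Key secondary 3 is the same comparison without the first 2 weeks of each period.

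**Population.** SAP 10.2: "The analysis will be conducted over the Full Analysis Set from the first two treatment sequences". SAP 4.5 admits "All subjects in the Safety Set who have at least 1 post-baseline" primary efficacy assessment, with no exposure condition overall or per period.

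**Test.** Key secondary 1 comes second in the fixed order (SAP 10.3). The lower limit of the exact 95% CI is compared with 0.2.

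**Related rules.**
- The dropout imputation in SAP 10.5.2 is a sensitivity analysis of the primary endpoint.
- The key secondary analyses are repeated in the Per-protocol Set, which takes subjects "who complete scheduled primary assessments for 6 study weeks" and have none of the deviations listed in SAP 19.4.

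**The concern.** P_R compares two rates within a subject, and the rule lets one of them rest on a handful of days. With no attack in those days the active NNA is 0, which is a 100% reduction for anyone with at least one placebo attack. Score and drug effect then come apart: what is mostly measured is how short the observation was. The subjects concerned are those who did not stay on active treatment.

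The plan handles the same subjects differently elsewhere. SAP 10.5.2 treats dropout for adverse events, death or lack of efficacy as missing not at random and imputes from the worst quarter of observed values. Key secondary 1 can count such a subject as a success.

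Three neighbouring cases are also unsettled:
- An A/B subject who stops during Period 1 has no placebo NNA, and SAP 10.2 does not say how that subject enters the proportion.
- A very short placebo period containing an attack inflates the placebo NNA and makes a response easy.
- For key secondary 3, a stop within the first 14 days of a period leaves no evaluable days, so NNA is 0/0.

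**Working it through.** **1. The plan's own figure.** Protocol 9.6 claims more than 90% power for key secondary 1 with 44 subjects (0.44 against 0.2, one-sided 0.025). The one-sample chi-square formula gives

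Φ[(0.24 − 1.96·√(0.16/44)) / √(0.2464/44)] = Φ(1.63) = 94.8%.

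The exact rule (at least 15 of 44) gives 93.1%. The claim reproduces.

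**2. What the rule does to one subject.** Let y be the placebo attacks in 98 days and a the attacks in d days on active. The subject is a responder if y ≥ 1 and a ≤ 0.5·y·d/98. At d = 7 this is a ≤ y/28, so in practice zero attacks are needed. One attack gives NNA 30.4/7 = 4.3 (30.4/3 = 10.1 at day 3), and response would then need 28 placebo attacks.

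**3. Chance of being scored a responder with no drug effect.** Assumptions: Poisson attacks at the same rate r per month on both treatments. Entry requires at least 2 per month; 3 and 4 are added as a range.

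P = Σ over y ≥ 1 of Pois(y; 98r/30.4) × P[Pois(rd/30.4) ≤ 0.5·y·d/98]

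| Days on active | 2/month | 3/month | 4/month |
|---|---|---|---|
| 3 | 82% | 74% | 67% |
| 7 | 63% | 50% | 40% |
| 14 | 40% | 29% | 28% |
| 98 | 14.5% | 8.8% | 6% |

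The day-7 entries are almost exactly the chance of no attack: exp(−2·7/30.4) = 0.63 and exp(−3·7/30.4) = 0.50.

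**4. Effect on the test, n = 52** (26 + 26 randomized, all kept in the denominator). The exact lower limit is 0.187 for 16 responders and 0.203 for 17, so 17 are needed.
- No early stopper, true P_R = 0.2: P[Bin(52, 0.2) ≥ 17] = 2.2%.
- One early active stopper scored at 50%: 0.5·P[Bin(51, 0.2) ≥ 17] + 0.5·P[Bin(51, 0.2) ≥ 16] = 0.5·0.0177 + 0.5·0.0368 = 2.7%.
- Two, by the same mixture: 3.4%. Scored at 63% instead: 3.0% with one, 4.0% with two.

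**5. How many to expect.** The documents give no count. SAP 2.5 plans for 44 completers in the crossover sequences, so 52 − 44 = 8 losses over both sequences and 28 weeks. Spread evenly (an assumption), B/A subjects in the first 6 weeks of Period 2 would number 8 × ½ × 6/28 ≈ 0.9, and in the first week alone 8 × ½ × 1/28 ≈ 0.14.

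**6. Does the Per-protocol repeat remove them?** The 6 study weeks in SAP 4.6 are not stated per period, so 14 weeks of placebo may satisfy them. Item 18 of SAP 19.4 (compliance below 85%) applies only with at least 6 weeks of treatment in the period. Item 19 (three or more consecutive missed doses) would catch an early stopper if doses after discontinuation count as missed, which it does not say.

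**The case against.** **The rule cuts both ways.** This stands. One attack in a few days makes a non-responder of a subject who might have done well. The upward pull comes only from zero attacks being the likelier result at very short exposure, and at 4 per month it is no longer the likelier result by day 7.

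**A reader might infer that the type I error roughly doubles.** With four such subjects scored at 50% the pass rate is 5.2%. But four is half of all planned crossover losses, falling in about one week of one sequence. The calculation also gives the stoppers a no-effect 50% while the other 48 respond at 0.2. Kept within the 3-per-month no-effect model (48 at 8.8%, 4 at 50%), the pass rate is about 0.003%; at 2 per month it is about 0.6%. The documents do not support a large inflation.

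**A reader might infer that the Per-protocol repeat leaves these subjects in.** Item 19 may exclude them, so the text is ambiguous rather than silent.

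**Limited stakes.** Key secondary 1 is tested only after the primary endpoint succeeds, and study success rests on the primary alone. The opening of SAP 10.5.1 was not available for this review, so a further sensitivity analysis cannot be excluded. It would not change the confirmatory definition in SAP 10.2.

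The core is unaffected: applying SAP 10.1 and 10.2 as written produces the scoring described.

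**Conclusion.** The point holds in limited form. It is a stated rule that gives an unsuitable score, not merely missing detail: a B/A subject with placebo attacks who stops active after a few attack-free days is a responder in a confirmatory endpoint. For such a subject the score says little about the drug (50% to 63% at day 7 against 9% to 14% for a full period, assuming no effect and 2 to 3 attacks per month). For the test the effect is modest: from 2.2% to 2.7% with one such subject and 3.4% with two, at a true P_R of 0.2 and n = 52. These figures rest on assumed Poisson rates and an assumed number of early stoppers, which may be zero. The 0/0 case in key secondary 3 and the scoring of a subject without a usable placebo period are undefined and need a rule whatever the count.

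**What to change.** In SAP 10.2, before unblinding, state for key secondary 1 and 3:

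1. A subject who discontinues during the active period before a pre-specified minimum exposure counts as not meeting P_R. Six weeks in that period is one possibility, to be presented as a choice, since the Per-protocol wording is not clearly per period.
2. A subject with no evaluable active days (for endpoint 3, none after day 14) also counts as not meeting P_R.
3. The same minimum applies to the placebo-period NNA. For example, one attack in 7 placebo days gives an NNA of 4.3, so up to 7 attacks in 98 active days (NNA 2.2) would pass as a 50% reduction.
4. Subjects with no usable placebo period are scored as non-responders in the main analysis, as the conservative rule, and excluded in a sensitivity analysis. This counts an A/B subject who completed active but has no placebo data as a failure, so it should be stated openly as a choice.
5. All A/B and B/A Full Analysis Set subjects stay in the denominator, and the present scoring is reported as a sensitivity analysis.

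It would also help to say in SAP 4.6 and item 19 of SAP 19.4 whether the 6 weeks are per period and whether doses after discontinuation count as missed.

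**Cost.** SAP wording and one derivation flag. P_R can only stay the same or fall. At a true 0.44 and n = 52, exact power falls from 96% to about 91% if 4 subjects are forced to non-response, and to about 81% if all 8 planned crossover losses were.

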10.2 Key Secondary Efficacy Variable(s) and Analysis

The key secondary efficacy variables are listed as following:

- 1. The proportion of subjects meeting the criterion of at least a 50%, 70%, 90% and 100% reduction in the NNA during the 2000 IU C1 esterase inhibitor [human] liquid for injection treatment period relative to the placebo period.
- 2. The NNA excluding the first 2 weeks of each treatment period.
- 3. The proportion of subjects meeting the criterion of at least a 50%, 70%, 90% and 100% reduction in the NNA for the 2000 IU C1 esterase inhibitor [human] liquid for injection treatment period relative to the placebo period excluding the first 2 weeks of each treatment period.

Key secondary efficacy endpoints 1 and 3 are defined as achieving a \geq 50% reduction in the NNA (P_R) during the 2000 IU C1 esterase inhibitor [human] liquid for injection treatment period relative to the placebo period.

The Key secondary endpoints 1 and 3 will be analyzed as the proportion of subjects meeting the above clinical response criterion (P_R). The analysis will be conducted over the Full Analysis Set from the first two treatment sequences. The null hypothesis is that P_R is less than or equal to 0.2, and the alternative hypothesis is that P_R is greater than 0.2 as below:

$$H_{0:} P_{R} \leq 0.2$$
vs
$$H_{1:} P_{R} > 0.2$$

The proportion P_R will be estimated with an exact 95% CI. The lower limit of the 95% CI for the proportion will be compared with 0.2. This is equivalent to testing the null hypothesis against the alternative hypothesis at a 1-sided alpha level of 0.05 using the binomial distribution.

Analysis of key secondary endpoint 2 will follow the same methods (ie, the linear mixed effect model) used for the primary efficacy endpoint.

The key secondary analyses will be performed using the Full Analysis Set and the Per-protocol Set.

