9.6 Sample Size Calculation and Power Considerations

For the primary efficacy endpoint, the NNA, a sample of 44 subjects from the crossover sequences will provide approximately 90% power at an alpha level of 0.025 (1-sided) to detect a difference of 1.0 attacks per month between active treatment and placebo assuming a between-subject standard deviation of 2.0. This target is supported by the recently completed, dose-ranging, Phase 2 study with CINRYZE (0624-206).

Regarding the analysis of the key secondary endpoint, the proportion meeting criterion P_R relative to placebo, 44 subjects will provide >90% power to test the hypothesis H_0 : proportion ≤ 0.2 against H_1 : proportion > 0.2 , assuming the true proportion is 0.44 by using a 1-group Chi-square test at an alpha level of 0.025 (1-sided).

Previous communications have occurred between regulatory authorities and the sponsor regarding a Phase 3 study for the SC CINRYZE development program. The regulatory authority indicated that the Phase 3 study should be of sufficient size to have a 95% probability for detection of safety signals occurring with an incidence of 5% or greater of subjects.

With respect to safety, a Safety Analysis Set of 60 subjects ensures that if the true population event proportion of any subject with a particular event is at least 5%, then the probability of observing at least 1 such event in the Safety Analysis Set is >95%.

The sample size calculation was conducted using nQuery + nTerim 2.0.

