2.5 Determination of Sample Size

The enrollment goal for this study is to randomize at least 66 subjects to ensure 54 subjects complete both treatment periods (44 for the crossover sequences, 10 for the active/active sequence).

For the primary efficacy endpoint, the normalized number of angioedema attacks (NNA), a sample of 44 subjects will provide 90% power at an alpha level of 0.025 (1-sided) to detect a difference of 1.0 attacks per month between active treatment and placebo assuming a standard deviation of the difference of 2.0.

Regarding the analysis of the key secondary endpoint, the proportion meeting criterion P_R relative to placebo, 44 subjects will provide 90% power to test the hypothesis H_0 : proportion

Page 18

 \leq 0.2 against H₁: proportion >0.2, assuming the true proportion is 0.44 by using a 1-group Chi-square test at an alpha level of 0.025 (1-sided).

With respect to safety, a Safety Analysis Set of 60 subjects ensures that if the true population event proportion of any subject with a particular event is at least 5%, then the probability of observing at least 1 such event in the Safety Analysis Set is >95%.

The sample size calculation was conducted using nQuery + nTerim 2.0.

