10.3 Adjustments for Multiplicity

To control the overall type 1 error, the primary and key secondary endpoints will be tested at the 0.05 significance level in the pre-specified order of the primary endpoint, key secondary endpoint 1, key secondary endpoint 2, and key secondary endpoint 3. Once one hypothesis test is not significant, the significance of all subsequent tests will not be assessed. The determination of a successful study is based solely on the results of the primary endpoint analysis regardless of the results for the key secondary endpoints.

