16. CHANGES TO ANALYSES SPECIFIED IN PROTOCOL

Not applicable.

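### SAP 10.2 labels the key secondary responder test 1-sided 0.05, but its exact 95% CI rule is a 1-sided 0.025 test

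*SAP*

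**What the plan says.** Key secondary endpoints 1 and 3 are the proportions of subjects whose normalized number of attacks is at least 50% lower on active treatment than on placebo. Endpoint 3 leaves out the first 2 weeks of each period. The null hypothesis is that the proportion is 0.2 or less.

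- **SAP 10.2, decision rule.** The proportion is estimated with an exact 95% interval. "The lower limit of the 95% CI for the proportion will be compared with 0.2".
- **SAP 10.2, next sentence.** "This is equivalent to testing the null hypothesis against the alternative hypothesis at a 1-sided alpha level of 0.05 using the binomial distribution".
- **Protocol 9.8.2.1.** It has the same interval rule, described as "equivalent to testing the null hypothesis against the alternative hypothesis at a 1-sided alpha level of 0.025 using the normal approximation to the binomial distribution".
- **Power statements.** Protocol 9.6 sizes this endpoint "by using a 1-group Chi-square test at an alpha level of 0.025 (1-sided"), and SAP 2.5 uses the same level: "Chi-square test at an alpha level of 0.025 (1-sided").
- **Primary endpoint, SAP 10.1.** "The upper confidence bound of 95% CI must be less than 0 in order for C1 INH to be considered superior to the placebo". This is also a 1-sided 0.025 criterion.
- **Multiplicity, SAP 10.3.** "the primary and key secondary endpoints will be tested at the 0.05 significance level in the pre-specified order". Sidedness is not given.
- **SAP section 16, changes from the protocol.** "Not applicable".

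**The concern.** SAP 10.2 gives a decision rule and an alpha level for the same test, and the two do not agree. The SAP does not say which prevails. The protocol and both power statements point to 1-sided 0.025, and section 16 records no deliberate change of level.

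An analyst who follows the interval rule keeps the 1-sided error at or below 0.025. An analyst who computes an exact binomial p-value and compares it with the stated 0.05 is also following the text, but can declare success with one responder fewer at most sample sizes. The reported interval could then include 0.2 beside a p-value called significant.

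The test order makes this more than a labelling matter. Key secondary 1 comes directly after the primary endpoint, and testing stops at the first non-significant result. A disputed result on endpoint 1 therefore decides whether endpoints 2 and 3 may be tested at all.

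**Working it through.** **Inputs**

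- Null proportion 0.2 and exact two-sided 95% interval: SAP 10.2.
- Planned proportion 0.44 and 44 crossover subjects: SAP 2.5 and protocol 9.6.
- Randomized to the two crossover sequences: 26 + 26 = 52 (SAP Table 1, protocol Table 7).
- Range of analysed sizes, n = 40 to 52: my assumption, to cover some loss below 44 and up to all 52 randomized.

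**Step 1. What level does the interval rule have?**

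The exact (Clopper-Pearson) lower limit L for r responders out of n solves P(X ≥ r | n, L) = 0.025. That probability rises with L, so L lies above 0.2 exactly when P(X ≥ r | n, 0.2) is below 0.025. The rule is therefore an exact binomial test at 1-sided 0.025. Checked over every r for n = 20 to 80, the interval rule and the 1-sided 0.025 test never disagree. The interval rule and a 1-sided 0.05 test disagree at 60 combinations of n and r. The 0.05 in SAP 10.2 does not reproduce.

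**Step 2. Cut-offs at the planned sizes**

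| n | responders | observed | P(X ≥ r given 0.2) | 95% lower limit | 90% lower limit | interval rule | 1-sided 0.05 |
|---|---|---|---|---|---|---|---|
| 44 | 14 | 31.8% | 0.0436 | 0.1861 | 0.2037 | fail | pass |
| 44 | 15 | 34.1% | 0.0203 | 0.2049 | 0.2233 | pass | pass |
| 52 | 16 | 30.8% | 0.0436 | 0.1872 | 0.2035 | fail | pass |
| 52 | 17 | 32.7% | 0.0215 | 0.2033 | 0.2202 | pass | pass |

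The full 95% intervals at the disputed counts are 18.6% to 47.6% for 14/44 and 18.7% to 45.1% for 16/52. In both rows the 90% lower limit is above 0.2, which shows that the 0.05 label belongs to a 90% interval. The true error of each rule is the tail probability at its cut-off:

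- n = 44: 2.03% under the interval rule, 4.36% under the label.
- n = 52: 2.15% under the interval rule, 4.36% under the label.

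**Step 3. Other sample sizes**

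Minimum responders (interval rule / 1-sided 0.05):

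| n | 40 | 41 | 42 | 43 | 44 | 45 | 46 | 47 | 48 | 49 | 50 | 51 | 52 |
|---|---|---|---|---|---|---|---|---|---|---|---|---|---|
| cut-offs | 14/13 | 14/14 | 15/14 | 15/14 | 15/14 | 15/15 | 16/15 | 16/15 | 16/15 | 17/16 | 17/16 | 17/16 | 17/16 |

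The two differ by one responder at 11 of the 13 sizes and agree at n = 41 and n = 45.

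**Step 4. How likely is the disputed count?**

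This is the binomial probability of exactly 14/44 or 16/52:

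- At the planned 0.44: 0.0327 (n = 44) and 0.0176 (n = 52).
- At 0.30, a value I assume to show sensitivity and which the documents do not give: 0.1239 and 0.1183.

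**Step 5. Does the power statement favour either level?**

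With n = 44 and 0.2 versus 0.44, the normal-approximation power is

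Φ{[√44 × 0.24 − z × √(0.2 × 0.8)] / √(0.44 × 0.56)}.

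- With z = 1.960 (1-sided 0.025) this is 94.8%.
- With z = 1.645 (1-sided 0.05) it is 97.0%.
- Exact power under the interval rule, P(X ≥ 15 | 44, 0.44), is 93.1%.

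The protocol claims more than 90% and the SAP says 90%. The 0.025 level supports either statement, so nothing in the sample size requires 0.05.

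**The case against.** The strongest reply is that the faulty sentence only describes the rule. SAP 10.2 gives one operative instruction, the interval comparison, and that instruction is right and matches the protocol. SAP 10.2 asks for no p-value for this proportion, so harm arises only if someone sets the interval aside and programs the description. At the planned 0.44 the disputed count is unlikely, and study success rests on the primary endpoint alone. All of this is true, and it limits the weight of the point. It does not make the sentence correct: a stated threshold for a gatekeeping test is wrong, and a reader has to look outside SAP 10.2 to see which number to trust.

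A second reply is that the unsided 0.05 in SAP 10.3 supports the label. It does not. Read as two-sided 0.05, it agrees with every other statement. No reading of it makes a 95% interval equivalent to a 1-sided 0.05 test.

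A third reply is that the protocol sentence used as the reference is itself imprecise, because it equates an exact interval with a normal approximation. That stands. An uncorrected score test with null variance at 1-sided 0.025 needs one responder fewer than the exact rule at 8 of the 13 sizes from n = 40 to 52 (40, 42, 43, 46, 47, 49, 50 and 51). The cut-offs agree at n = 44 and n = 52, but n = 44 is a near tie: 14 responders give z = 1.9598 against a critical value of 1.9600. The SAP's move to the binomial distribution is therefore an improvement, and the protocol is the reference here for the alpha level only.

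**Conclusion.** The concern holds. The alpha label in SAP 10.2 is wrong; the interval rule beside it is right. The label conflicts with that rule, with protocol 9.8.2.1 and with the power statements in protocol 9.6 and SAP 2.5.

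Applying the label instead of the rule would lower the bar by one responder at most plausible sizes and roughly double the true 1-sided error (at n = 44, from 2.03% to 4.36%). It could also open key secondaries 2 and 3 after a result that the interval rule calls a failure. The primary endpoint and the success criterion are untouched. The practical risk is small if the responder proportion is near 0.44 and larger if it is nearer 0.30, which is an assumed value. The figures take each analysed subject as one independent binomial observation, with 40 to 52 subjects analysed. This should be corrected, but it is not a threat to the trial.

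**What to change.** 1. **SAP 10.2:** replace the sentence with one saying that the interval comparison is an exact binomial test at 1-sided alpha 0.025. Leave the exact 95% interval rule as it is.
2. **SAP 10.3:** write the level as 2-sided 0.05 (1-sided 0.025). The same unsided wording stands in the protocol synopsis and in protocol 9.8.1, and this SAP clarification settles how it is to be read.
3. **SAP section 16:** record that the exact binomial test is the operative one, and that the normal approximation named in protocol 9.8.2.1 is not strictly equivalent to the exact interval.

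The cost is one sentence, one phrase and one note, made before unblinding. No protocol amendment is needed for this, because the protocol's rule and alpha level stay as they are. Design, data collection and sample size do not change.
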